9.4.2 Secondary outcomes

The secondary clinical outcomes will be knowledge and self-efficacy pre-and post-EFCT data for all implementation team members. Items will be completed prior to the start of the EFCT for each team member and after the completion of the EFCT.

To assess feasibility and fidelity as a component of our second objective, we will track the following:

- Number of residents each NH is able to engage in the program via data collected from the Resident Preferences Worksheet.
- Alignment of important preferences with activities on the Resident Preferences Worksheet; we will review for appropriateness.
- How many implementation team members complete the EFCT based on data from the EFCT LMS.
- Implementation fidelity with a standardized Pragmatic Checklist that a site champion will use to observe an IPPI session by each care partner
- Response to the intervention by the resident for each IPPI, care partners will record when an IPPI was conducted in the EMR.
- Amount, frequency, and duration of IPPI delivery to determine if the recommended 2 sessions per week over the course of 6 months were implemented with the EMR.
- Acceptability, feasibility, and appropriateness of the intervention will be calculated for staff in both the EFCT post-test and the exit interview (Weiner et al., 2017; AIM, IAM, and FIM measures).
- Facilitators and barriers to implementation in the Exit interview with participating implementation team members.

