Subject Identification	Identify residents who score 0-12 on the BIMS with either a non-zero score on one of 5 Section D Mood items or a non-zero score on Section E Behaviors from MDS 3.0 upon completion of a scheduled annual or quarterly MDS 3.0 assessment.	That 15-20 residents with both of these criteria are engaged during the pilot timeframe per NH community - approximately 3-8 residents per month
Implementation team identified	Recommended Activity Director and DON, and CNAs or activity personnel who care for residents identified	That 3-5 staff volunteer from each community to lead and deliver IPPI activities
Orientation to IPPI	Virtual Coaching session	Does champion/team attend orientation Yes/No measured by Project Director
Emotion-Focused Communication Training	Recommended champion(s) and care partners (e.g., CNAs/Activity personnel) complete on-line, self-paced, interactive education session prior to initiating implementation	That all of the identified implementation team completes training as identified in the learning management system
Learn how to conduct an IPPI protocol	Watch IPPI training videos, review tip sheets on considerations before, during, and ending an IPPI	Binder for champion to record if activity was completed or not
Match Resident Preferences with IPPI protocols	Review Section F of MDS 3.0 to identify resident important preferences and review IPPI Protocols on website Identify 1-2 protocols for use with resident	Completion of the Resident Preference Worksheet and EMR

Intervention Structure	Implementation Strategy	Implementation Measure
Care Conference Discussion	Identify targeted behavior to be addressed with IPPI and who will be the primary IPPI delivery care partner	Obtain a deidentified print out of the care plan and look for documentation of targeted behavior and care partner
Identify and procure IPPI supplies needed	Managing supplies – what is needed, where will they be stored, identified	Exit interview and Resident Preferences Worksheet
Assess Fidelity to IPPI protocol	Champion does one IPPI with each resident while care partner watches, then champion watches while care partner conducts one and documents if IPPI steps followed	Observation by champion is documented with the Pragmatic Checklist
Assess Adherence to IPPI protocol and participant responsiveness	Conduct two 10 min IPPIs per week over the course of 6 months (e.g., 48 sessions total)	Documentation of each of 48 IPPIs completed for each resident in EMR

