6.2.2 Enrollment, Baseline, and/or Randomization

Enrollment

There will be a waiver of consent for all residents enrolled in the program. Upon identification of eligibility, the implementation team uses the Resident Preferences Worksheet to identify next steps. This will be a rolling process as individuals are identified as eligible to participate. Each enrolled individual will have a Worksheet completed at their specific time of enrollment. In this Worksheet, members of the implementation team will identify the resident's important preferences and identify matching IPPI protocols that can be used. They will also identify the behavior they hope to target with the IPPI intervention. A copy of the care plan will be obtained to ensure that the targeted behavior is addressed. The PI will collect this Worksheet from champions to determine whether or not the IPPI protocols were appropriately matched to important resident preferences as a measure of implementation fidelity every three months.

Baseline Assessments

The baseline assessment for residents will be their most recent MDS 3.0 (either

annual or quarterly). The BIMS and Section D/Section E responses will be provided to the PI for each enrolled resident by the UCH IT professionals. These data will include the targeted mood or behavior selected by care partners at enrollment. The type of mood or behavior item being targeted will be different for each resident (e.g., wandering for one, verbal behavior for another).

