To assess feasibility and fidelity as a component of our second objective, we will track the number of residents each NH is able to engage in the program via data collected from the Resident Preferences Worksheet. This worksheet also tracks alignment of important preferences with activities; we will review for appropriateness. We will track how many implementation team members complete the EFCT based on data from the EFCT LMS. We will also provide a standardized Pragmatic Checklist that site champion(s) will use to observe an IPPI session by each care partner to establish implementation fidelity. This short checklist incorporates learning from the online trainings into a Yes/No format to ensure that good communication practices are utilized. Each checklist item is equal to one point and a total number of points will be calculated to assess the fidelity to the intervention process. Each care partner delivering the IPPI will be observed once with each resident by an implementation team member. Care partners will record the date and how long the IPPI session lasted in the EMR. This documentation will be used to report on the amount, frequency, and duration of IPPI delivery to determine if the recommended 2 sessions per week over the course of 6 months were implemented. Further, participant responsiveness to the IPPI protocol will be measured through the question "*Would you like to do this activity again?*" posed to residents upon completion of an IPPI activity and recorded in the EMR. Finally, acceptability, feasibility, and appropriateness will be calculated by staff in both the EFCT post-test and the exit interview (Weiner et al., 2017; AIM, IAM, and FIM measures). Qualitative data will be collected to determine facilitators and barriers in the Exit interview with participating implementation team members.

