10.2 Data Management

MDS 3.0 data for all residents will be provided to the PI by UCH IT Professionals. [name] will identify participating/enrolled residents and extract distress (Section D and Section E) MDS 3.0 data at 3-months and 6-months post enrollment date and transmit data with face identifiers such as name, SSN, and HIC removed prior to statistical consultant via a secure file transfer.

Data collection forms will be provided to the site champion(s) for completion in a binder including the a) Implementation team training documentation, b) Resident Preferences Worksheet, and the c) Pragmatic Observation Checklist. For the resident preferences worksheet, site champion(s) will maintain a password protected list of the name of each resident that is enrolled into the IPPI program along with a unique ID# that is determined by the champion(s). This password protected file will be shared with the PI who will then

link the data from this worksheet to the electronic medical record data prior to deidentifying.

The statistical consultant on the project will receive de-identified data from the PI via a secure file electronic transfer.

Staff completing the EFCT will be prompted to answer questions within the EFCT LMS before and after completion of the training. These data will be extracted from Qualtrics, de-identified by the PI, and provided to the statistical consultant.

At the Exit Interviews, the PI and Project Manager will conduct a primarily qualitative interview that will help to answer secondary objectives.

Qualitative interviews will be audio-recorded, transcribed in otter.ai, and then uploaded into Dedoose, a qualitative data analysis software, and provided to the statistical consultant for coding.

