***email address will be used to identify if individual completed the Emotion Focused Communication Training**

IPPI Program – Resident Preferences Worksheet

Site champion(s) will maintain a password protected list of the name of each resident that is enrolled into the IPPI program along with a unique ID# that is determined by the champion(s). This password protected file will be shared with the PI who will then link the data from this worksheet to the electronic medical record data prior to deidentifying.

After completing a resident's preference assessment, identify and record their most important preferences in the column "Important Preferences." Next, review the list of IPPI protocols then record the protocols that match the resident's important preferences in the "Matching IPPIs" column. Review the list of matching IPPIs with the implementation team member(s) that will be facilitating the activity with the resident and let them chose which IPPI activities (1-2) they are most comfortable doing. After they've chosen the IPPI activities, record their selection in the "IPPIs Selected" column. Identify one or more resident behaviors that are the target outcome for the intervention as indicated on the MDS Section E. Finally, note if the resident completed the project and if there were any adverse events.

Resident Unique ID#	Important Preferences	Matching IPPIs	IPPIs Selected by implementation team	Supplies Needed Location	Which targeted behavior(s) do you hope the IPPI will remediate? Check all that apply	Did the resident complete the IPPI Project? Yes No If no, why did the individual not complete the project?	Did the resident have any adverse events? Yes No If Yes, complete Serious Adverse Event Report Form
	•	•	•	○	 Physical behavioral symptom  Verbal behavioral symptom  Other behavioral symptom  Rejection of Care  Wandering  Depressive Mood Symptoms	○	○

Observation Checklist of Fidelity to IPPI Protocol conducted by Champion

Did the person delivering the IPPI do any of the following?

1. Yes No N/A Introduce self to resident
2. Yes No N/A Introduce IPPI activity to resident
3. Yes No N/A Consider possible distractions (background noise, visual/tactile)
4. Yes No N/A Check that individual could hear or was wearing hearing aids if applicable
5. Yes No N/A Interrupt resident in the middle of a visit (reverse coded)

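### Preference alignment is judged within one site-completed worksheet, with no planned check against MDS Section F ratings and no named record of which protocol was delivered

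*Combined protocol and SAP*

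**What the plan says.** Section 3 makes the 16 preference items in MDS Section F the starting point for choosing activities. The matching row of Table 1 tells sites to "Review Section F of MDS 3.0 to identify resident important preferences".

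Section 9.4.2 lists the fidelity measure as "Alignment of important preferences with activities on the Resident Preferences Worksheet; we will review for appropriateness". Section 6.2.2 has the PI collect the worksheet and "determine whether or not the IPPI protocols were appropriately matched to important resident preferences as a measure of implementation fidelity every three months".

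The worksheet in Appendix A has three columns that bear on this. Staff are told to "identify and record their most important preferences in the column" provided for them, next to "review the list of IPPI protocols then record the protocols that match" those preferences, and then to enter the one or two activities that the delivering staff choose from the matching list.

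On data reaching the PI, Section 6.2.2 says: "The BIMS and Section D/Section E responses will be provided to the PI for each enrolled resident by the UCH IT professionals". Section 10.2 says that MDS data for all residents go to the PI, who will then "extract distress (Section D and Section E) MDS 3.0 data at 3-months and 6-months post enrollment date". On sessions, Section 9.1 says: "Care partners will record the date and how long the IPPI session lasted in the EMR". It adds the resident's answer on whether they would repeat the activity.

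**The concern.** Section 2.2 rests the program on matching activities to preferences the resident has expressed. Section 11.2 says that activities of this kind are usually part of standard care, but in groups. One-to-one delivery and preference match are therefore what set IPPI apart, and fidelity belongs to the second objective.

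The planned check compares entries on one form, and the form's instructions lead staff to make those entries agree. The resident's own ratings and the activity actually delivered sit outside the comparison. If either departs from the worksheet, the fidelity report would not show it. Section 9.2 says that findings from this pilot will guide adaptations for a full-scale trial, so a weak measure of this component could be carried forward.

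**Working it through.** The documents give no target, rate or threshold for alignment, so there is no figure to reproduce. The check is to look in each planned data source for something that could show a mismatch.

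**Sources**
- Worksheet (Appendix A): preferences, matching protocols and selected protocols. It has no field for a Section F item or rating. It has no per-session field, although the schedule in 6.1 marks the worksheet at each IPPI.
- PI review (6.2.2, 9.1, 9.4.2): reads that form for appropriateness, with no scoring rule or denominator.
- MDS (6.1, 6.2.2, 10.2): BIMS and Sections D and E are named; Section F is not.
- EMR session entry (9.1): date, length and wish to repeat. No field for the protocol is named. Table 1 gives the measure for the matching step as completion of the worksheet and EMR, without saying what EMR content is meant.
- Observation checklist (Appendix A): none of the 17 items asks whether the activity fits a preference, and 6.1 limits it to the first IPPI.
- Care plan (Table 1): checked for targeted behavior and care partner.
- Section 9.5: no analysis of alignment.

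**Three ways the match can fail**
1. A listed preference is paired with a protocol that does not suit it. The PI can see this on the worksheet.
2. A preference is listed that the resident did not rate as important, and is then paired well. The worksheet looks aligned. Only Section F would show the error.
3. The worksheet is right, but another activity is delivered. Only a session-level record of the protocol would show it.

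The plan as described covers the first and not the other two.

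**Scale**
Sessions = residents × 48 (48 from Table 1 and the adherence section; 105 to 110 residents from the Précis).
- 105 × 48 = 5,040
- 108 × 48 = 5,184
- 110 × 48 = 5,280

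Against these stands one worksheet row per resident, 105 to 110 rows.

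**What a Section F comparison would add**
The documents give no rate of agreement between worksheet and Section F, so I assume 60%, 80% and 95% for illustration. The Wilson 95% interval is (p + z²/2n ± z√(p(1−p)/n + z²/4n²)) / (1 + z²/n), with n = 108 and z = 1.96. For p = 0.80:
- centre: (0.80 + 0.0178)/1.0356 = 0.790
- half-width: 1.96 × 0.0395/1.0356 = 0.075

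| Assumed agreement | 95% interval |
|---|---|
| 60% | 50.6% to 68.7% |
| 80% | 71.5% to 86.5% |
| 95% | 89.1% to 97.8% |

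These intervals ignore clustering within the 7 homes. A resident-level comparison would separate the 60% case from the 95% case clearly. The worksheet alone cannot separate any of them, because the second column is filled in to match the first.

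**The case against.** The strongest reply is that the plan is less closed than it looks, and several stronger readings do go too far.

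- A reader might infer that one champion writes both sides of the comparison. The documents do not settle this. Section 10.1 assigns the form to the delivering care partner, 6.2.2 to implementation team members, and the introduction to Section 16 to any member but mainly the champions. The form is site-completed in every case.
- A reader might infer that Section F never reaches the PI. Sections 10.2 and 11.2 describe MDS data for all residents and an unfiltered extract of the provider's system, so Section F may already be in hand. What can be said is that no use of it is planned.
- A reader might infer that the check cannot fail, or that agreement will be near 100%. No document gives such a figure. The PI is outside the homes and may reject a poor pairing among more than 60 protocols.
- A reader might infer that no session can ever be classified as matched. The EMR template is not in the documents, so the protocol may be recorded without being mentioned.
- A reader might infer that this gap is what prevents a clinical result from being tied to preference-based activity. A single-group, descriptive pilot could not do that with any fidelity measure.

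It is also fair that fidelity has other measured parts: an observed first session, dose, duration and responsiveness. Section 5.1 has champions assess the Section F preferences once eligibility is known, so the ratings extracted must be those used for matching. Changing a clinical record mid-study is a real burden.

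These points narrow the concern. None of them supplies a planned comparison with Section F, a named field for the delivered protocol, or an alignment analysis.

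**Conclusion.** The point holds in this form: preference alignment is a named fidelity outcome, but it is reviewed within a single site-completed worksheet. That review can find a poor pairing. It cannot find a preference wrongly listed as important, or delivery of an unmatched activity. On the fields named, the measure describes what was planned for about 105 to 110 residents and says nothing about the match in roughly 5,040 to 5,280 sessions.

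The conclusion assumes that the EMR entry holds no protocol identifier beyond what 9.1 describes. If it does hold one, the delivery half of the gap closes once its use is written into the plan. The Section F half remains either way. The effect is confined to one secondary outcome, and the primary clinical outcome is untouched. It deserves correction because the component concerned defines the intervention and a better check uses routinely collected data.

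**What to change.** 1. In 6.2.2 and 10.2, name the baseline Section F items among the data the PI extracts, with the date of the assessment used for matching.
2. In 9.4.2 and 9.5, define alignment as the share of enrolled residents whose selected protocols (the *IPPIs Selected* column) map to a Section F preference rated important. Use a protocol-to-item map fixed before the data are examined. State how a resident with two selected protocols or missing Section F data is counted. Report the PI's appropriateness review alongside.
3. Confirm whether the EMR session entry records the protocol delivered. If it does, or if a code can be added, also report the share of delivered sessions that matched. If not, describe the measure as planned alignment, not delivered alignment. Say in Table 1 what the EMR contributes to the matching measure.
4. Reconcile 6.2.2, 10.1, the introduction to Section 16 and Appendix A on who completes the worksheet.

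The cost is one map of more than 60 protocols to 16 items; Section 3 already says the protocols address all 16. If a code is added, it takes a few seconds per session and a change to the provider's record. Sessions recorded before such a change could be assessed at worksheet level only. No visit or resident assessment is added.

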9.5 Data Analyses

Analysis of data will be descriptive. To address our first objective of clinical impact for residents, we will code a change score for each enrolled resident's targeted behaviors (e.g., improved, stayed same, worsened) in two ways. We will use the MDS 3.0 data between baseline and 6 months. We will report aggregate percentages of improved, stayed same, and worsened from the MDS 3.0 data. For implementation team members, the outcomes of knowledge and self-efficacy will be analyzed through paired samples t-tests of pre- and post-EFCT test measures.

For our second objective of feasibility and fidelity, we will calculate the number of residents each NH is able to engage as a percentage of the goal (e.g., 15 residents minimum) via data collected from the Resident Preferences Worksheet. We will also calculate the percentage of the implementation team that completed the EFCT based on data from the EFCT LMS. Finally, we will calculate the average number of IPPIs completed (via the EMR). Acceptability, feasibility, and appropriateness will be calculated according to responses from the exit interview (Weiner et al., 2017; AIM, IAM, and FIM measures). Qualitative data collected by the semi-structured exit interview

will be audio recorded, transcribed verbatim, and coded for facilitators and barriers in Dedoose.

